- 2. Mean absolute difference in the number of skin tears at baseline and 30 days after the last treatment
- 3. The changes in collagen and elastin between untreated and treated skin
- 4. Mean absolute difference in the change in epidermal thickness between treated and untreated skin
- 5. Changes in gene expression between treated and untreated skin

Population: Sample size 10

Male and female adults over the age of 21 living in Palm Beach

County Florida.

Number of Sites 1

Study Agent: Sciton's BBL

Study Duration: 51 days

SCHEMATIC OF STUDY DESIGN

Day -30 to 0 Screening

- •Total n=10
- Obtain informed consent
- Screen potential subjects by inclusion and exclusion criteria (Eligibility Questionnaire)

Day 0: Randomization

•Subjects randomized to have BBL on either their left or right

Day 0: Baseline assessments/ Study Intervention

• Baseline Assessments:

Pre-procedure pictures of patient's lower arms taken with a Digital Camera

Baseline assessment and measurement by evaluator

Baseline Medical History and Medication questionnaires completed by all subjects

• Study Intervention #1:

Sciton's BBL done according to purpura protocol on one arm according to randomized assignment

• Post-Procedure Assessments:

Post-procedure questionnaires filled out by all subjects

Day 1: Follow-up assessments

• At Home Follow-up Assessments Questionnaire Regarding Side-Effects

Day 2: Follow-up assessments

• At Home Follow-up Assessments Questionnaire Regarding Side-Effects

Day 7 +/- 2 Days: Follow-up assessments / Study Intervention

Follow-up assessments:

Evaluator assessment and measurement

Pictures taken of subject's lower arms

Subject follow up questionnaires filled out by all subjects

• Study Intervention #2:

Sciton's BBL done a second time on the assigned arm according to protocol settings

• Post-Procedure Assessments:

Day 14 +/- 2 Days: Follow-up assessments / Study Intervention

• Follow-up assessments:

Evaluator assessment and measurement Pictures taken of subject's lower arms

Subject follow up questionnaires filled out by all subjects

• Study Intervention #3:

Sciton's BBL done a third time on the assigned arm according to protocol settings

• Post-Procedure Assessments:

Post-procedure questionnaires filled out by all subjects immediately after treatment

Day 21 +/- 2 Days: Follow-up assessments / Study Intervention

• Follow-up assessments:

Evaluator assessment and measurement

Pictures taken of subject's lower arms

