6 STUDY PROCEDURES AND SCHEDULE

6.1 STUDY PROCEDURES/EVALUATIONS

6.1.1 STUDY SPECIFIC PROCEDURES

- Medical history obtained and verbally verified
- Assigned arm meeting inclusion criteria is shaved to remove all hair
- Digital Pictures taken of bilateral hands and arms
- Counseling the subjects on the treatment that they will be receiving and post-care instructions.
- The study coordinator will check before the patient leaves that all appropriate photos and paperwork have been completed.
- BBL study treatment will be done according the protocol below outlining specific settings

BBL Only Protocol

1st Treatment Settings

- 1. SkinTyte Filter ST: 150 Joules, 15msec, 15 degrees for 10 continuous passes in alternating directions (5 each direction)
- 2. 590 Filter: 8J, 15msec, 15 degrees x 2 passes
- 3. 590 Filter: 10J 15msec, 15 degrees x 2 passes
- 4. 560 Filter: 8J, 15msec, 15 degrees x 2 passes

2nd Treatment Settings

If any answers on the post procedure side effects questionnaire from day 0,1, or 2 were SEVERE or if the patient had blisters from the previous treatment

Decrease Step 3 & 4 by 2 Joules

1. SkinTyte Filter ST: 150 Joules, 15msec, 15 degrees for 10 continuous passes in alternating directions

- 2. 590 Filter: 8J, 15msec, 15 degrees x 2 passes
- 3. 590 Filter: 8J 15msec, 15 degrees x 2 passes
- 4. 560 Filter: 6J, 15msec, 15 degrees x 2 passes

If any answers on the post procedure side effects questionnaire on day 0,1, or 2 were MODERATE with NO blistering

Decrease Step 3 & 4 by 1 Joule

- 1. SkinTyte Filter ST: 150 Joules, 15msec, 15 degrees for 10 continuous passes in alternating directions
- 2. 590 Filter: 8J, 15msec, 15 degrees x 2 passes
- 3. 590 Filter: 9J 15msec, 15 degrees x 2 passes
- 4. 560 Filter: 7J, 15msec, 15 degrees x 2 passes

If all answers on the post procedure side effects questionnaire on day 0,1, or 2 protocol were MINIMAL

Keep Settings the same as previous visit

- 1. SkinTyte Filter ST: 150 Joules, 15msec, 15 degrees for 10 continuous passes in alternating directions (5 each direction)
- 2. 590 Filter: 8J, 15msec, 15 degrees x 2 passes
- 3. 590 Filter: 10J 15msec, 15 degrees x 2 passes
- 4. 560 Filter: 8J, 15msec, 15 degrees x 2 passes

If all answers on the post procedure side effects questionnaire on day 0,1, or 2 protocol were NONE

Increase Step 1 by 10 additional passes and Increase Step 3 & 4 by 1 Joule

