6.2.2 ENROLLMENT/BASELINE

Enrollment/Baseline Visit (Visit 1, Day 0) Treatment #1

- Review in depth the study design with subjects and obtain informed consent of potential participants verified by signature
- Perform examination and verbally review subject's medications, medical history, and subject questionnaire to determine eligibility based on inclusion/exclusion criteria

- Obtain demographic information
- Shave the hair on the subjects' lower arms
- Take digital pictures of subjects' lower arms
- Have evaluator measure the size and number of bruises and skin tears
- Perform the BBL treatment on assigned arm per protocol
- Record adverse events as reported by participant or observed by investigator
- Perform protocol adherence check by study coordinator
- Expected post-procedure side effects and possible emergent situations reviewed with subjects and post-op written instructions given

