8.5 MEASURES TO MINIMIZE BIAS

ENROLLMENT/ RANDOMIZATION/ MASKING PROCEDURES

In order to avoid bias, the subjects will be randomized to receive treatment on either their left or right arm. All evaluators of pictures will be blinded as to which technique was used on which side. In order to avoid bias, the evaluator will not be the primary investigator.

To ensure only the clinical investigator performing the procedures and the study coordinator know

the assignment of arms, each subject will have an envelope assigned to them to be held by the study coordinator with the subject's name on the outside and the assignment on the inside. Only during treatments does the study coordinator allow the clinical investigator to see the inside of the envelope.

The skin biopsy samples will be coded to ensure blinded analysis.

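### The protocol does not consistently place eligibility confirmation and the baseline lesion measurement before the treated side is known, and it describes no allocation concealment from the study coordinator

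*Combined protocol and SAP*

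**What the plan says.** The documents describe allocation and the Day 0 sequence in four places. The SAP pages add nothing on allocation.

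- **Schematic of Study Design.** The Day -30 to 0 box includes "Screen potential subjects by inclusion and exclusion criteria (Eligibility Questionnaire". A separate Day 0 box follows: "Subjects randomized to have BBL on either their left or right". Only after that comes "Day 0: Baseline assessments/ Study Intervention", which contains the photographs and "Baseline assessment and measurement by evaluator".
- **Section 6.2.2 (Visit 1, Day 0).** The list runs: consent; "Perform examination and verbally review subject's medications, medical history, and subject questionnaire to determine eligibility based on inclusion/exclusion criteria"; demographics; shaving of the lower arms; pictures; "Have evaluator measure the size and number of bruises and skin tears"; then BBL on the assigned arm. It has no randomisation step.
- **Section 6.1.1.** "Assigned arm meeting inclusion criteria is shaved to remove all hair" stands in the bullet before the pictures. Sections 3.1 and 6.2.2 shave both arms.
- **Section 8.5.** "each subject will have an envelope assigned to them to be held by the study coordinator with the subject's name on the outside", with the assignment inside. The treating investigator and the study coordinator are the only people meant to know the side, and the investigator is shown it only during treatments. The evaluator is not the primary investigator. Explicit blinding is stated for those who evaluate pictures.

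The documents do not say who generates the sequence, how, when the envelope is prepared, or whether it is sealed, opaque or numbered. Nor do they require eligibility and baseline to be final before the side is known.

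**The concern.** The primary endpoint (section 3.2.2) is the between-arm difference in change from baseline in lesion number and area, measured in the five purpura subjects. Ecchymoses are visible and come and go (section 2.1). Anyone who knows the treated side can therefore see whether that arm looks worse or milder than the other on the day.

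Suppose entry, or the baseline reading, leaned towards cases where the assigned arm looks worse. That arm would then tend to drift back to its usual level by Day 51 with no treatment effect at all, and the drift would look like benefit. Subtracting baseline does not remove this bias, because the bias sits in the baseline value. The issue arises before treatment and is separate from whether the evaluator stays masked afterwards.

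**Working it through.** **Step 1: order of events.** The plan has no sample-size or alpha figure to reproduce (section 8.4 is marked not applicable), so the first check is a comparison of the texts.

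| Question | Schematic | 6.2.2 | 6.1.1 | 8.5 |
|---|---|---|---|---|
| Side assigned before baseline measurement? | Yes, by box order | Not stated; assigned arm first appears at treatment | Assigned arm named in the bullet before the pictures | Not stated |
| Side assigned before the eligibility examination? | Questionnaire screening comes first; examination not shown | Not stated | Not stated | Not stated |
| Arms shaved | Not stated | Both | Assigned arm only | Not stated |
| Who may know the side | Not stated | Not stated | Not stated | Coordinator; treating investigator at treatment |

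The schematic and 6.2.2 do not fix one order, and 6.1.1 conflicts with 3.1 and 6.2.2 on shaving. If 6.1.1 were followed, the single shaved arm could reveal the side to whoever photographs and measures at baseline.

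**Step 2: what selection on the side would do.** Monte Carlo with no BBL effect, 60,000 trials per setting.

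- From the documents: 5 purpura subjects (Précis, section 3.1); paired t-test on the between-arm difference in change (section 8.1). The average of 15 lesions per subject is the starting mean of a small topical growth-factor study cited in section 2.1.
- Assumed: gamma subject means with CV 0.5; arm rates multiplied by exp(+a) and exp(-a), with a ~ N(0, SD 0.2); independent Poisson counts at baseline and Day 51 with unchanged rates; at least one lesion per arm; subjects whose assigned arm has fewer lesions than the other at baseline are excluded with probability p.
- Statistic per subject: d = (Day 51 - Day 0) on the treated arm minus (Day 51 - Day 0) on the control arm. Test: t = mean(d) / (SD(d)/√5) on 4 degrees of freedom. Negative values favour BBL.

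| p | False shift (lesions) | Rejection, one-sided 5% | Rejection, two-sided 5% |
|---|---|---|---|
| 0 | 0.0 | 4.8% | 4.4% |
| 0.25 | -0.35 | 6.1% | 4.7% |
| 0.50 | -0.76 | 8.3% | 5.3% |
| 1 | -2.1 | 19.9% | 11.0% |

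Repeat runs agree to within about half a percentage point (19.4% to 19.9% one-sided and 10.8% to 11.0% two-sided at p = 1). With 15 lesions per subject an arm averages 15/2 = 7.5, so the extreme shift is 2.1/7.5 = 28% of an arm's count. Averages of 6 and 30 lesions at p = 1 give shifts of -1.36 and -2.66 and one-sided rejection of 19.2% and 17.2%.

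**Step 3: a second model.** Let the between-arm baseline difference be standard normal with correlation ρ to the Day 51 difference, and let a share q of subjects enter only when the assigned arm looks worse. The expected false benefit is q(1 - ρ)E|Z|, with E|Z| = 0.798. For q = 1 and ρ = 0.5 this is 1 × 0.5 × 0.798 = 0.40 SD, and simulation gave 0.401. One-sided 5% rejection for n = 5, over ρ from 0.8 down to 0.2, is 6.0% to 7.5% at q = 0.2, 8.0% to 13.0% at q = 0.5 and 12.4% to 28.4% at q = 1. At q = 0 it is 4.9% to 5.1%.

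Both models give no bias when the side plays no part in entry or in the baseline reading.

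**The case against.** The strongest reply is that the protocol already contains real safeguards and that harm requires conduct nobody has shown.

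- The treating investigator sees the side only during treatments. The evaluator who measures lesions is outside the two roles allowed to know it. **This stands**, apart from the shaving conflict in 6.1.1 and the explicit blinding being worded for picture evaluators only.
- The coordinator's documented duties are checks of paperwork, photographs and adherence, plus holding the envelopes. No role in deciding entry or in measuring is described. **This stands** as a limit on the likelihood. It does not supply concealment.
- The lesion criterion in section 4.1 applies to each arm, and each subject is their own control, so selection on general prognosis cannot bias the comparison. **This stands.** Selection on which arm looks worse that day still could.
- The bullets in 6.1.1 are not strictly chronological: counselling follows the pictures, and the check before the patient leaves precedes the treatment bullet. **This stands**, so 6.1.1 shows a conflict and does not prove early assignment.
- This is a ten-subject pilot with no stated alpha and 95% intervals, so a one-sided false-positive rate is a weak measure of harm. **This largely stands.** At two-sided 5% there is almost no inflation up to 50% exclusion. The shift in the estimate remains whichever test is used.

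A reader might infer that the side is randomised before the Day 0 eligibility examination. The documents do not say so: questionnaire screening precedes randomisation in the schematic, and 6.2.2 leaves the order open. A reader might also infer that the side could steer the date of Day 0. Randomisation is itself dated Day 0, visits are scheduled at screening (section 6.2.1), and no envelope preparation time is given, so this is unsupported. Nor can silence on sealing and numbering be read as proof that assignments could be swapped unnoticed. It shows only that protection is not described.

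**Conclusion.** The point holds as a gap in specification and concealment. The order of randomisation relative to eligibility confirmation and baseline measurement is not consistently fixed, one section could unmask the baseline evaluator, and concealment from the coordinator is absent. It would go too far to say that enrolment and baseline are unprotected, since section 8.5 keeps the side from the evaluator and, until treatment, from the treating investigator.

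Bias arises only if knowledge of the side influences entry or the baseline reading. How far that might happen is purely an assumption, so the shifts and rejection rates above are conditional illustrations and do not predict what this trial will show. The direction is clear (in favour of BBL), and the remedy is cheap enough that the change should be made although its likely effect is unknown.

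**What to change.** Reconcile the schematic and sections 6.1.1, 6.2.2 and 8.5 so that Day 0 runs in one order:

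1. Consent.
2. Eligibility confirmed and recorded.
3. Both lower arms shaved; photographs taken; the evaluator's lesion count and area for both arms recorded as final.
4. Only then, the next sealed, opaque, sequentially numbered envelope is opened and the assigned arm treated.

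In section 8.5, replace the name-labelled envelope with numbered envelopes prepared by the statistician already named in the protocol, from a computer-generated list that the statistician keeps. The study ID and time of opening are written on each envelope, no number is reused, and later envelopes stay sealed, so the coordinator does not know an upcoming assignment.

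Cost: wording changes in four places, ten envelopes and a few minutes on Day 0. No extra visit, procedure or subject is needed.

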9 ETHICS/PROTECTION OF HUMAN SUBJECTS

9.1 ETHICAL STANDARD

The investigator will ensure that this study is conducted in full conformity with Regulations for the Protection of Human Subjects of Research codified in 45 CFR Part 46, 21 CFR Part 50, 21 CFR Part 56, and the ICH E6.

9.2 INFORMED CONSENT PROCESS

Informed consent is required for all participants. In obtaining and documenting informed consent, the investigator will comply with applicable regulatory requirements and will adhere to 45 CFR Part 46, 21 CFR Part 50, 21 CFR Part 56, and ICH GCP. Prior to the written informed consent, the consent forms will be provided to the participants. Consent forms describing in detail the study agent, study procedures, and risks will be given to the participant and written documentation of informed consent is required prior to starting intervention/administering study product.

The investigator will explain the research study to the participant and answer any questions that may arise. All participants will receive a verbal explanation in terms suited to their comprehension of the purposes, procedures, and potential risks of the study and of their rights as research participants. Participants will have the opportunity to carefully review the written consent form and ask questions prior to signing. The participants will have the opportunity to think about being a participant prior to agreeing to sign. The participant will sign the informed consent document prior to any procedures being done specifically for the study. The participants may withdraw consent at any time throughout the course of the trial. A copy of the informed consent document will be given to the participants for their records. The rights and welfare of the participants will be protected by emphasizing to them that the quality of their medical care will not be adversely affected if they decline to participate in this study.

9.3 PARTICIPANT AND DATA CONFIDENTIALITY

Participant confidentiality is strictly held in trust by the participating investigators, their staff, and the sponsor(s) and their agents. Therefore, the study protocol, documentation, data, and all other information generated will be held in strict confidence. No information concerning the study or the data will be released to any unauthorized third party without prior written approval of the sponsor.

The study monitor, other authorized representatives of the sponsor, representatives of the IRB or pharmaceutical company supplying study product may inspect all documents and records required to be maintained by the investigator, including but not limited to, medical records for the participants in this study. The clinical study site will permit access to such records.

The study participant's contact information will be securely stored at each clinical site for internal use during the study. At the end of the study, all records will continue to be kept in a secure location for as long a period as dictated by local IRB and Institutional regulations.

Study participant research data, which is for purposes of statistical analysis and scientific reporting, will be transmitted to and stored at the Siperstein Dermatology Group Boynton research office. This will not include the participant's contact or identifying information. Rather, individual participants and their research data will be identified by a unique study identification number. The study data entry and study management systems used by clinical sites and by Siperstein Dermatology Group research staff will be secured and password protected. At the end of the study, all study databases will be de-identified and archived at the Siperstein Dermatology's Boynton Beach research office.

9.3.1 RESEARCH USE OF STORED HUMAN DATA

Pictures and data collected under this protocol may be used in future publications. Access to stored pictures and data will be stored using codes assigned by the investigators. Data will be kept in password protected computers. Only investigators will have access to the samples and data.

10 DATA HANDLING AND RECORD KEEPING

10.1 DATA COLLECTION AND MANAGEMENT RESPONSIBILITIES

Data collection is the responsibility of the clinical trial staff at the site under the supervision of the site PI. The investigator is responsible for ensuring the accuracy, completeness, legibility, and timeliness of the data reported.

All source documents will be completed in a neat, legible manner to ensure accurate interpretation of data. Black ink is required to ensure clarity of reproduced copies. When making changes or corrections, cross out the original entry with a single line, and initial and date the change.

Clinical data (including AEs, concomitant medications, and expected adverse reactions data) will be entered into a 21 CFR Part 11-compliant data capture system. The data system includes password protection and internal quality checks, such as automatic range checks, to identify data

that appear inconsistent, incomplete, or inaccurate. Clinical data will be entered directly from the source documents.

10.2 STUDY RECORDS RETENTION

Study documents will be retained for a minimum of 2 years after the formal discontinuation of the clinical study. These documents will be retained for a longer period, however, if required by local regulations. No records will be destroyed without the written consent of the sponsor, if applicable. It is the responsibility of the sponsor to inform the investigator when these documents no longer need to be retained.

10.3 PROTOCOL DEVIATIONS

A protocol deviation is any noncompliance with the clinical trial protocol. The noncompliance may be either on the part of the participant, the investigator, or the study site staff. As a result of deviations, corrective actions are to be developed by the site and implemented promptly. It is the responsibility of the site to use continuous vigilance to identify and report deviations within 7 working days of identification of the protocol deviation, or within 7 working days of the scheduled protocol-required activity. All deviations must be addressed in study source documents, reported to the IRB and sponsor. The site PI/study staff is responsible for knowing and adhering to their IRB requirements.

11 CONFLICT OF INTEREST POLICY

The independence of this study from any actual or perceived influence, such as by the pharmaceutical industry, is critical. Therefore, any actual conflict of interest of persons who have a role in the design, conduct, analysis, publication, or any aspect of this trial will be disclosed and managed. Furthermore, persons who have a perceived conflict of interest will be required to have such conflicts managed in a way that is appropriate to their participation in the trial.

